4.4.4. Non-COVID ICU admissions 1st January 2020 – 1st July 2020

All emergency ICU admissions between 1st January 2020 and 1st July 2020 where the primary diagnosis was not COVID-19. This cohort includes patients admitted to ICU concurrently to the primary COVID-19 cohort. While this cohort will likely be small, it will possibly provide a fairer comparison of outcomes if the pandemic did affect the healthcare provision during follow-up (i.e. if there were a reduction in the number of hospital admissions for non-Covid causes during the period of the pandemic due to restrictions).

5. Analysis

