11.4. Analysis populations

Primary group

Our primary group will be patients admitted with confirmed COVID-19 between 1st January to 1st July 2020.

Comparator groups

The primary comparator group will be patients admitted to ICU with viral or bacterial pneumonia between 1st July 2016 and 1st July 2019.

Secondary comparator groups will include:

- All emergency ICU admissions between 1st July 2016 and 1st July 2019
- All emergency ICU admissions between 1st July 2016 and 1st January 2020 where the primary diagnosis was not COVID-19
- All emergency ICU admissions between 1st January and 1st July 2020 where the primary diagnosis was not COVID-19

Pregnant patients

We will undertake a sub-group analysis in patients who were pregnant when treated for COVID-19 on ICU between 1st January and 1st July 2020.

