4.1. Eligibility

- 4.1.1. Inclusion Criteria
 - Age ≥16 years
 - Admitted to an adult, general ICU in England or Wales as an emergency (i.e. unplanned)
 - Admitted to ICU for either:
 - \circ $\,$ confirmed COVID-19 between 1st January to 1st July 2020 $\,$
 - without confirmed COVID-19 between 1st July 2016 and 1st July 2020 (patients admitted prior to 2020 are included to account for seasonal variation and identify specific impacts of the pandemic on patient follow-up)

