4.4. Cohort definitions

4.4.1. Patients with confirmed COVID-19 between 1st January to 1st July 2020 This group will consist of all individuals who were admitted to an intensive care unit between 1st January and 1st July 2020 with a confirmed diagnosis of COVID-19.

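### The concurrent 2020 comparator is selected on primary diagnosis and the COVID-19 cohort on confirmed infection, so the rules as written can overlap and conflict with the eligibility criteria.

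*SAP*

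**What the plan says.** The COVID-19 cohort is defined by confirmed infection. SAP 4.4.1 takes everyone admitted to intensive care in the first half of 2020 "with a confirmed diagnosis of COVID-19". Protocol 11.4 agrees: "Our primary group will be patients admitted with confirmed COVID-19 between 1st January to 1st July 2020". Neither asks that COVID-19 be the primary diagnosis.

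The concurrent comparator is defined by primary diagnosis. SAP 4.4.4 takes every emergency admission in the same months "where the primary diagnosis was not COVID-19", under a heading that begins "Non-COVID ICU admissions". Protocol 11.4 lists it as a secondary comparator: "All emergency ICU admissions between 1st January and 1st July 2020 where the primary diagnosis was not COVID-19".

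The eligibility criteria use a third form. SAP 4.1.1 admits patients to the study through one of two limbs. One is admission to ICU for "confirmed COVID-19 between 1st January to 1st July 2020". The other is admission "without confirmed COVID-19 between 1st July 2016 and 1st July 2020". Protocol 8.2 has the same two limbs.

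**The concern.** Having confirmed COVID-19 and having a primary diagnosis other than COVID-19 are not opposites. A patient can have both, for example a trauma or stroke admission with a positive test. An analyst who programs the two cohort sentences as they stand would place that patient, and any later death, in both groups.

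SAP 4.4.4 offers this cohort as a possibly fairer comparison if the pandemic changed healthcare provision during follow-up, so its definition matters. SAP 5.4.3 then makes cohort status the dependent variable of the propensity model and matches one to one on the score. A patient held twice has the same covariates in both records, hence the same score, and could be matched to their own record. Such a pair carries no information about COVID-19. The cluster-robust standard errors planned in SAP 5.4.3 allow for dependence within pairs but do not remove this bias. The unadjusted models in SAP 5.4.2 would also count one death on both sides.

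**Working it through.** **1. The rules side by side.** Take an adult emergency admission between January and July 2020 who was discharged alive, had confirmed COVID-19, and had another primary diagnosis.

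| Place | Selection rule | Is this patient in? |
|---|---|---|
| SAP 4.4.1; Protocol 11.4, primary group | Confirmed COVID-19 | Yes |
| SAP 4.4.4; Protocol 11.4, third secondary comparator | Primary diagnosis other than COVID-19 | Yes |
| SAP 4.1.1 and Protocol 8.2, first limb | Admitted for confirmed COVID-19 | Depends on how strictly *for* is read |
| SAP 4.1.1 and Protocol 8.2, second limb | No confirmed COVID-19 | No |

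The result depends on how the sections are combined:
- If the two limbs only define one eligible population, and section 4.4 then selects from it, the patient is in both cohorts.
- If each cohort is tied to its own limb and *for* is read loosely, the patient is in the COVID-19 cohort only.
- If each cohort is tied to its own limb and *for* is read strictly, the patient is in neither.

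No section says which applies.

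**2. The plan's own figure.** SAP 2.2 and Protocol 11.3 give 90,000 × 3.5 = 315,000, and 315,000 + 4,600 = 319,600. This reproduces. The total does not count the 2020 comparator, so it stays the same whichever wording is used. (Both documents call 4,600 90% of about 5,000. In fact 0.90 × 5,000 = 4,500, and 4,600 is 92%. The difference does not matter here.)

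**3. Possible overlap.** The documents give no count. For scale only, assume that a share f of the 4,600 had another primary diagnosis:
- f = 0%: 0 patients
- f = 2%: 0.02 × 4,600 = 92
- f = 5%: 0.05 × 4,600 = 230
- f = 10%: 0.10 × 4,600 = 460

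**4. Effect on the matched contrast.** Assume that all 4,600 are matched, that every duplicated patient is paired with their own record, and that one-year risks are p1 = 15% (COVID-19) and p0 = 10% (comparator), a true risk ratio of 1.50. Duplicated patients are given risk p1. Then

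risk ratio = p1 / [(1 − f) × p0 + f × p1]

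- f = 2%: 0.15 / (0.098 + 0.003) = 1.485
- f = 5%: 0.15 / (0.095 + 0.0075) = 1.463
- f = 10%: 0.15 / (0.090 + 0.015) = 1.429

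With the risks reversed (10% v 15%, true ratio 0.667), f = 10% gives 0.10 / (0.135 + 0.010) = 0.690. The ratio moves towards 1 either way, because a self-pair adds the same risk to both arms.

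**5. Effect on the unadjusted contrast.** The comparator's size is not given. With an assumed 10,000 to 45,000 patients, 460 duplicates would be 4.6% to 1.0% of it. Putting those shares in place of f, with p1 = 15% and p0 = 10%:
- 4.6%: 0.15 / (0.0954 + 0.0069) = 1.466
- 1.0%: 0.15 / (0.099 + 0.0015) = 1.493

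Here the move towards 1 depends on the duplicated patients having a risk close to that of the other COVID-19 patients.

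**The case against.** The strongest reply is that eligibility already settles the matter. The cohort definitions in SAP 4.4 do not repeat the age limit or survival to discharge, so they appear to operate inside the population set by SAP 4.1. That section's second limb bars confirmed cases, and the heading of SAP 4.4.4 says non-COVID. The Protocol synopsis draws the same line between patients treated for COVID-19 and those treated for another acute condition. The primary-diagnosis phrase also appears in SAP 4.4.3 for admissions up to 1 January 2020, where it excludes almost nobody, so it may be shorthand. This is good evidence of intent. A reader might infer that the plan definitely puts patients in both arms, and the documents do not support that. What remains is that the sentence an analyst would program says something else in both documents, and nothing ranks it below the eligibility criteria.

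A reader might also infer that this is the only comparator followed up during the pandemic. It is not. Patients in SAP 4.4.3 admitted late in 2019 are followed through 2020. The July 2019 cut-off in SAP 4.4.2 protects only six months. The exploratory comparison with other respiratory infections (SAP 1.2, Protocol 6) is also concurrent.

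Finally, a reader might suppose that matching would preferentially draw in the duplicated patients. Each would be an exact match for their own record, but nothing shows that they resemble other COVID-19 patients. Trauma or stroke admissions may well not.

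**Conclusion.** The comparator rule in SAP 4.4.4 and Protocol 11.4 is wrong as written. It conflicts with the plan's own eligibility criterion and, taken literally, admits exposed patients to the control group. Overlap is permitted by the wording, not shown to occur.

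The effect is probably modest. Under the assumptions above, 0 to 460 patients would be duplicated, and a true risk ratio of 1.50 would fall to no lower than about 1.43 in the matched analysis. The overlap share, the one-year risks, the comparator size and complete self-pairing are all assumptions.

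Only the concurrent 2020 comparison is touched, and Protocol 11.4 lists it as secondary. The Protocol's primary comparator (pneumonia, July 2016 to July 2019) and the other cohort ending 1 July 2019 are unaffected by this wording. The point should be corrected before the cohorts are programmed, but it does not threaten the main comparison.

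**What to change.** In SAP 4.4.4 and the matching line of Protocol 11.4, replace "where the primary diagnosis was not COVID-19" with the wording already used for eligibility: *without confirmed COVID-19*.

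Add one sentence stating that the COVID-19 cohort and the concurrent comparator are mutually exclusive per person, and saying where a confirmed case with another primary diagnosis belongs. Exclusivity has to be per person because someone with two eligible 2020 admissions, one without and one with COVID-19, could otherwise still enter both cohorts. Protocol 11.2 covers transfers between ICUs but gives no rule for choosing between separate admissions, so the sentence should say which admission counts.

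The exclusion should not be widened to COVID-19 confirmed at any time during the stay. That would be a new criterion based on information arising after ICU admission, and it is not needed to remove the conflict.

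The cost is one phrase in each document plus the exclusivity sentence. No new data are needed. The comparator becomes slightly smaller, and the stated total of 319,600 does not change.

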5.1. Baseline patient characteristics

We will describe the characteristics of patients at the time of ICU admission, including demographics and clinical characteristics (listed in Section 5.2). These will be presented for each cohort separately. Data will be presented as mean with standard deviation (SD) when normality distributed or median and interquartile range for skewed variables. Categorical variables will be presented as number and proportion.

5.2. Assumed confounding covariates

The following variables are assumed to be related to the risk of experiencing one or more of the outcomes, and will therefore be included in the baseline characteristics table, be included as covariates in the multivariable regression models, and be included as covariates in the propensity scores.

- Patient demographics: age, sex, ethnicity, index of multiple deprivation (IMD), body mass index (BMI), clinical frailty score, smoking status, month of admission, dependency prior to ICU admission (fully/partial/total assistance with activities of daily living), geographical region
- Medical history: comorbidities (as per Elixhauser (14)), dialysis-dependent, total length of previous hospital admissions in year prior to ICU admission.
- Hospital/ICU stay characteristics: Length of hospital stay prior to ICU transfer, Length of ICU stay, length of hospital stay after discharge from ICU, hospital region, month of admission.
- Acuity: APACHE-II/ICNARC severity score at admission, length of mechanical ventilation, length of advanced organ support (cardiovascular, respiratory, renal, liver, neurological)

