We will also analyse the data using propensity score matching as an alternative method to account for any potential confounding associated with the COVID-19 and comparator populations. A logistic propensity score will be used to create a matched population. The following variables will be considered for inclusion in the propensity score:

- Age at discharge from hospital
- Charlson/Elixhauser comorbidity index
- Ethnicity
- Illness severity (APACHE-II or ICNARC severity score) on admission to ICU
- Days of mechanical ventilation
- Week of the year of ICU admission (to account for potential increased survival over the course of the pandemic)

As an exploratory analysis, we will examine potential prognostic factors (such as patient or ICU treatment characteristics) for the primary and secondary outcomes. We will further investigate whether some of the secondary outcomes are time-varying predictors of mortality. Latent class analysis may also be used to identify any clustering of the secondary outcomes and their severity and/or timing.

Where common patient data items are available from multiple data sources (e.g. age, gender ethnicity), we will develop a standard protocol to resolve inconsistencies. Should substantial differences remain, we will explore any effect on our results through a sensitivity analysis.

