12.1. Source Data

This study requires accessing and linking confidential health care records. Access to these data will be subject to approval from a REC and Section 251 support from the CAG.

Data linkage

Eligible participants will be identified by ICNARC from the CMP audit. Each eligible participant will be assigned a pseudonymous “study key”. The study key will be sent to the other participating organisations for linkage alongside the following direct identifiers:

- Date of birth
- NHS number
- Postcode
- Sex/gender

Linkage will be performed by each participating organisation, following the principles of the NHS Digital matching algorithm, after which all direct identifiers will be removed. Only pseudonymised data (including the study key) will be securely transferred to the Sponsor (Critical Care Research Group, University of

Oxford), where researchers will assemble these data sources for analysis. At no point will direct identifiers be sent to the Sponsor.

Data sources

The following data sources will be linked to the CMP audit:

- NHS Digital
 - Hospital Episode Statistics (HES)
 - Admitted Patient Care
 - Outpatients
 - Maternity Services Data Set (MSDS)
 - Civil Registration (deaths)
 - Emergency Care Data Set (ECDS)
 - Hospital Episode Statistics Accident and Emergency
 - GPES Data for Pandemic Planning and Research (COVID-19)
- Patient Episode Database for Wales (PEDW)
- UK Renal Registry (UKRR)
- National Institute for Cardiovascular Outcomes Research (NICOR)
- Stroke Sentinel National Audit Programme (SSNAP)

The study will also link data from the UK Obstetric Surveillance System (UKOSS) to identify patients who were pregnant at the time of ICU admission. As UKOSS does not collect direct identifiers, it will be linked to the pseudonymous data set using probabilistic matching.

Data timeframes

On a per patient level, the study will request 5 years of diagnostic coding data prior to ICU admission (to accurately assess prior medical co-morbidities) and 1 year post hospital discharge (to assess the outcomes of this study). The use of a 5 year window of prior diagnostic coding data is based on previous literature that has shown this enhances data accuracy (14). This is preferable to relying solely on the diagnostic coding relating to the hospital admission, as complications cannot be differentiated from prior co-morbidities (15).

Data storage for analysis

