5.3.2. Secondary outcomes

Cause-specific readmissions will be identified by combining HES (ICD-10) and GDPPR coding, using coding sets defined in Ayoubkhani et al. (15). For a venous thrombotic event, we will include the following ICD-10 codes: I80.0-I80.3, I80.8-I80.9, I82.9, O22.2-O22.3, O87.0-O87.1, I26.0, and I26.9.

• Emergency hospital admission – any non-elective hospital admission. Recorded in the hospital episode statistics data set.

- Emergency hospital admission for respiratory infection any emergency hospital admission for a respiratory infection.
- Emergency hospital admission for a major adverse cardiac event (myocardial infarction, stroke, acute heart failure)
- Emergency hospital admission for a venous thrombotic event (deep vein thrombosis or pulmonary embolism)
- Development of end stage renal failure treated by renal replacement therapy

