5.4.3. Comparison of COVID-19 cohort to other cohorts using propensity score matching

For each comparison of the COVID-19 cohort to a non-COVID cohort we will use propensity score matching to create cohorts that are similar in terms of baseline characteristics and confounding variables. We will construct a propensity score using logistic regression where the outcome is the cohort status, and the covariates will be those previously defined in Section 5.2. The model will allow for non-linear relationships between continuous variables and the outcome. The propensity score will then be estimated for each patient. One to one matching will be performed based on the

propensity score, initially using a nearest neighbour (greedy) approach. We will assess the balance achieved through the matching process using standard approaches, such as Q-Q plots, and assessments of the absolute standardised mean difference. If the covariates are not well balanced after nearest neighbour matching, alternative approaches will be tested, such as full matching, until sufficient balance is achieved. If sufficient balance cannot be achieved or too many patients from the COVID cohort are removed by the matching algorithm, we will consider using the propensity score for inverse probability weighting in our Cox regression models.

Once matched cohorts have been identified, we will analyse the outcomes with the standard regression modelling as described in Section 5.4.2– using Cox regression for the death outcome, and competing risk approaches for the secondary outcomes. However, since the data will now be clustered due to the matching, we will need to account for this in the regression models. We will therefore use cluster-robust standard errors.

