5.6. Sensitivity analyses

To assess the robustness of the propensity-matched analysis, we will also fit multivariable regression models. We will use restricted cubic splines or fractional polynomials to allow for potentially nonlinear relationships between continuous covariates and outcomes. The adjustment variables will be those listed in Section 5.2.

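### SAP 5.2 lists no separate history of the cardiac, thrombotic or respiratory-infection outcomes and measures prior hospital use only as total length of stay, so residual confounding of the secondary contrasts is possible

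*SAP*

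**What the plan says.** SAP 5.2 is the only place where the adjustment set is fixed. Its medical-history line reads "Medical history: comorbidities (as per Elixhauser (14)), dialysis-dependent, total length of previous hospital admissions in year prior to ICU admission". The section also lists demographic and lifestyle items, frailty, dependency, features of the hospital and ICU stay, and acuity. These variables are to appear in the baseline table and to "be included as covariates in the multivariable regression models, and be included as covariates in the propensity scores".

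The later sections refer back to that list. For the propensity score, SAP 5.4.3 says "the covariates will be those previously defined in Section 5.2". For the multivariable sensitivity analysis, SAP 5.6 says "The adjustment variables will be those listed in Section 5.2".

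The secondary outcomes in SAP 5.3.2 include "Emergency hospital admission for a major adverse cardiac event (myocardial infarction, stroke, acute heart failure") and "Emergency hospital admission for a venous thrombotic event (deep vein thrombosis or pulmonary embolism"), together with any emergency admission, emergency admission for respiratory infection, and end-stage renal failure.

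On data, Protocol 12.1 states that "the study will request 5 years of diagnostic coding data prior to ICU admission (to accurately assess prior medical co-morbidities"). Protocol 11.2 names "Charlson/Elixhauser comorbidity index" among the variables to be considered for the propensity score.

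**The concern.** A patient's own earlier event of the same kind is an obvious candidate confounder when cohorts are compared on readmission for that event. The SAP already acts on this for one outcome: dialysis dependence is history bearing on the renal endpoint. The cardiac, thrombotic and respiratory-infection outcomes have no named counterpart. All-cause emergency readmission has only a proxy, since total days in hospital do not show whether the stays were emergencies or how many there were.

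The SAP 4.4 comparator cohorts are broad groups of emergency ICU admissions, so a different burden of vascular disease or prior emergency use from COVID-19 survivors is plausible. If a difference remains after adjustment for the listed covariates, it would enter the cardiac, thrombotic and readmission hazard ratios. The sensitivity analysis in SAP 5.6 changes the method but not the covariates, so agreement between it and the matched analysis would offer no reassurance on this point. The baseline and balance tables would not show the imbalance as a separate item. Under SAP 3.1 these outcomes are reported as an effect size and 95% confidence interval, and the interval does not reflect residual confounding.

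**Working it through.** **The plan's own figure.** The only derived number is the sample size: 90,000 x 3.5 + 4,600 = 315,000 + 4,600 = 319,600, which reproduces. (90% of 5,000 is 4,500; 4,600 is 92%. The difference is immaterial here.) The documents give no effect size, power, event rate or prevalence of prior events. Apart from the 4,600, every input below is an assumption.

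**Does any listed item cover the history?**
- Renal outcome: dialysis dependence is listed.
- Any emergency readmission: only total length of prior-year admissions, a partial proxy.
- Cardiac, thrombotic and respiratory-infection outcomes: no named item. The Elixhauser comorbidities may capture some of this history, but neither document prints the conditions in that set.

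**Size of bias if history is not captured.** For a binary confounder with prevalence p1 in the COVID-19 cohort and p0 in the comparator, and risk ratio RR between history and outcome,

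bias factor B = [1 + p1(RR - 1)] / [1 + p0(RR - 1)].

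A true ratio of 1.0 appears as B. The formula is for a risk ratio and is close to a hazard ratio when events are uncommon. If the listed covariates capture a share c of the log bias, the factor becomes B^(1-c).

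Assumed ranges: p1 5-10%, p0 10-30%, RR 2-4.

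| p1 | p0 | RR | B, nothing captured | half captured | 80% captured |
|---|---|---|---|---|---|
| 10% | 10% | any | 1.00 | 1.00 | 1.00 |
| 5% | 10% | 2 | 1.05/1.10 = 0.955 | 0.977 | 0.991 |
| 8% | 20% | 3 | 1.16/1.40 = 0.829 | 0.910 | 0.963 |
| 10% | 30% | 4 | 1.30/1.90 = 0.684 | 0.827 | 0.927 |
| 5% | 30% | 4 | 1.15/1.90 = 0.605 | 0.778 | 0.904 |

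The full span of these assumptions is 0.61 to 1.00, and it includes no bias. The factors fall below 1 only because the assumed prevalence is never higher in the COVID-19 cohort; exchanging p1 and p0 would give the reciprocals.

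**Comparison with sampling error.** For 1:1 matching with 4,600 per group and event risk r, d = 4,600r events per group and SE(log HR) is about sqrt(2/d). The 95% limits lie a factor exp(1.96 SE) either side of the estimate.

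| Assumed r | d | SE | factor |
|---|---|---|---|
| 1% | 46 | 0.209 | 1.51 |
| 3% | 138 | 0.120 | 1.27 |
| 5% | 230 | 0.093 | 1.20 |
| 30% | 1,380 | 0.038 | 1.08 |

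The middle scenario (0.829, a factor of 1/0.829 = 1.21) about equals the interval half-width at a 5% event risk and is smaller than it at 1% or 3%. With half captured it is 1/0.910 = 1.10, below the half-width at all three. For all-cause readmission at an assumed 30%, a modest imbalance (5% v 10%, RR 3: 1.10/1.20 = 0.917, a factor of 1.09) would already match the half-width of 1.08, although the formula is only approximate at that event risk.

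**The case against.** The strongest reply is that the gap may be smaller than it looks. Whether cardiac or thrombotic history is really absent depends on the contents of the Elixhauser set, which the documents cite but do not print. Age, smoking, body mass index, deprivation, frailty, dependency, acuity and prior length of stay are all adjusted for, and each may carry part of the missing history. The outcomes concerned are secondary and carry no p-values. For rare events, mid-range bias would be smaller than the sampling error. All of this stands and limits the point to possible residual confounding.

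A reader might infer more, in four ways that the documents do not support:
- **That the contrasts are confounded.** This needs an imbalance remaining after the listed covariates. No prevalence is given, and the assumed range includes none.
- **That COVID-19 would look safer.** The direction follows only from assuming more prior disease in the comparators. Protocol 11.4 names viral or bacterial pneumonia as the primary comparator, and SAP 1.2 keeps a respiratory-infection comparison. Nothing shows the direction for those groups or for the broader ones.
- **That the SAP removed an adjustment by leaving out Charlson.** Protocol 11.2 offered the two indices as alternatives to be considered, and the SAP chose one.
- **That no extra data could be needed.** The look-back is described as diagnostic coding, which supports the diagnoses directly. Counting emergency admissions needs the admission-method field for earlier stays. The linked HES/PEDW data and the length-of-stay covariate make this likely, but the look-back text does not state it.

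The reply does not answer the structural point. The list is closed, every adjusted analysis uses it, and the SAP does not say which listed item, if any, covers each outcome's history.

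**Conclusion.** The point holds as a gap in specification. Followed as written, the SAP leaves the count of prior emergency admissions unadjusted. It also leaves separately coded history of myocardial infarction, stroke, venous thrombosis and respiratory-infection admission unadjusted unless the Elixhauser definition happens to cover it. Residual confounding of the cardiac, thrombotic and readmission contrasts is possible, and the planned sensitivity analysis could not detect it.

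Size and direction are unknown. The 0.61 to 1.00 range rests wholly on assumed prevalences and risk ratios and on no capture by other covariates; it shows what is conceivable and does not estimate the bias. The sample size is unaffected, and no claim is made about the primary outcome.

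**What to change.** Add the following to SAP 5.2, so that they enter the propensity score, the multivariable models, and the baseline and balance tables:

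1. Indicators of prior myocardial infarction, prior stroke, prior deep vein thrombosis or pulmonary embolism, and prior respiratory-infection admission. Derive them by applying the SAP 5.3.2 outcome code lists to the 5-year look-back. The venous thrombosis codes are already printed there, and the other code sets are cited.
2. The number of emergency admissions in the year before the index admission, after confirming that the admission-method field is available for that year.

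Omit any indicator that the Elixhauser definition already captures, and say in SAP 5.2 which item covers it. Count only events before the index hospital admission, so that complications of that stay are not recorded as history; Protocol 12.1 makes the same distinction. Make the change before the analysis, so that the covariate list remains pre-specified.

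The cost is a few lines of SAP text and a few derived variables from data already requested, subject to the field check in item 2. Sample size and primary outcome do not change.

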4.1.2. Exclusion Criteria

The participant may not enter the study if ANY of the following apply:

• Patients who died in hospital after treatment on an ICU

We chose to exclude ICU admissions after 1st July 2020 to account for a possible three-month delay in patient data being registered in hospital episode statistics (HES) and national audit databases. Linking data sources in July and October 2021 will maximise the chance that complete data will be available for outcomes at 180 and 365 days respectively.

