5.4. Analysis methods

5.4.1. Descriptive analysis of incidence

The incidence of each of the primary and secondary outcomes will be summarised within each cohort. Kaplan-Meier curves will be used to graphically display the number of patients who die in the follow-up period, whilst cumulative incidence function curves will be used to display all of the secondary outcomes (treating death as a competing risk). The number and proportion of patients experiencing each event will be tabulated at each of the outcome assessment time points. Further analyses will investigate the event rates within relevant subgroups (described in Section 5.5). For continuous variables (such as age) we will additionally consider regression modelling with non-linear terms (e.g. fractional polynomials or restricted cubic splines) to describe the impact of the variable on the patient's risk of experiencing the outcome events.

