5.4.2. Comparison of COVID-19 cohort to other cohorts using standard regression modelling

To compare the risk of the primary outcome (death) between the COVID-19 cohort and the other cohorts, we will use Cox proportional hazards regression models to estimate the hazard ratio (and 95% confidence interval). The hazard ratio (HR) will be calculated at each of the outcome assessment time points. For the secondary outcomes, a competing risk approaches will be used, with death as the competing risk. We will use the cause-specific Cox proportional hazards regression approach to estimate the cause-specific hazard ratio (and associated 95% confidence interval). The Fine-and-Gray approach will be used as a sensitivity analysis to estimate the sub-distribution hazard ratio. For each of these analyses we will report unadjusted results.

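### The new end stage renal failure outcome is analysed in cohorts that include patients already on dialysis, who are handled only through a covariate

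*SAP*

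**What the plan says.** - **Outcome.** SAP 5.3.2 lists "Development of end stage renal failure treated by renal replacement therapy". SAP 1.2 and protocol sections 6 and 11.2 also word it as a new event. SAP 5.3.2 gives codes for venous events and cites code sets for cause-specific readmissions. For the renal outcome it states no requirement to be free of the condition at baseline, and does not say how continuing dialysis is counted.
- **Population.** The only exclusion criterion in SAP 4.1.2 is "Patients who died in hospital after treatment on an ICU"; protocol 8.3 is the same. SAP 4.4 defines the COVID-19 cohort without further restriction: "This group will consist of all individuals who were admitted to an intensive care unit between 1st January and 1st July 2020" with confirmed disease. The comparator cohorts are likewise all eligible emergency admissions.
- **Prior dialysis.** It appears only in SAP 5.2, under medical history: "dialysis-dependent, total length of previous hospital admissions in year prior to ICU admission". The listed variables go in the baseline table and are to "be included as covariates in the multivariable regression models, and be included as covariates in the propensity scores". Dialysis status is not a subgroup in SAP 5.5, and the sensitivity analysis in SAP 5.6 is covariate adjustment.
- **Analysis.** SAP 5.4.1: "The incidence of each of the primary and secondary outcomes will be summarised within each cohort". SAP 5.4.2, for secondary outcomes: "We will use the cause-specific Cox proportional hazards regression approach to estimate the cause-specific hazard ratio", and then "For each of these analyses we will report unadjusted results". Dialysis status does not enter either step.

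**The concern.** A patient on maintenance dialysis before ICU admission cannot newly develop treated end stage renal failure. Such patients are nevertheless in the denominators, the unadjusted models and the matched sets for this outcome. They can be handled in two ways, and the SAP does not choose between them. Either their continuing renal replacement after discharge is picked up as an event, or they sit in the risk set with no possibility of an event.

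On the first route, the reported incidence mixes old and new disease. A difference in chronic dialysis between the COVID-19 and comparator survivors would then look like a difference in new renal failure. Balancing dialysis status by matching does not cure this, because the same block of non-incident events is added to both arms and pulls the ratio towards 1. On the second route the effect is small, but the dialysis term in the multivariable model has no events behind it. The SAP's conclusion says pre-specification is meant to limit data-driven results, and here two permitted choices give very different answers.

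**Working it through.** **Figures in the plan.** The only related figure is the study size in SAP 2.2: 90,000 × 3.5 + 4,600 = 319,600, which reproduces. No dialysis prevalence, renal incidence or power is stated, so the inputs below are assumptions.

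**Assumed inputs.** Prevalence of prior dialysis p: 1% in COVID-19 survivors; 3% (or 5%) in comparators. True one-year risk r among those able to have the event: 1% (range 0.5% to 2%), equal in both cohorts, so the true ratio is 1.00.

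**Case A: patients already on dialysis never count as events.** Apparent risk = (1 − p) × r.
- COVID-19: 0.99 × 1% = 0.99%. Comparator: 0.97 × 1% = 0.97%.
- The crude ratio is 0.99/0.97 = 1.02, whatever r is. At 1% versus 5% it is 0.99/0.95 = 1.04.
- Incidence is diluted by p itself, that is by 1% to 3% in relative terms.

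**Case B: ongoing dialysis is counted as an event.** Apparent risk = p + (1 − p) × r.
- COVID-19: 0.01 + 0.99 × 0.01 = 1.99%. Comparator: 0.03 + 0.97 × 0.01 = 3.97%.
- The crude ratio is 1.99/3.97 = 0.50.

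| Prevalence, COVID-19 vs comparator | r = 0.5% | r = 1% | r = 2% |
|---|---|---|---|
| 1% vs 3% | 0.43 | 0.50 | 0.60 |
| 1% vs 5% | 0.27 | 0.33 | 0.43 |

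The direction is also assumed. With 3% in COVID-19 and 1% in comparators, the ratio at r = 1% is 3.97/1.99 = 1.99. With equal prevalence it is 1.00.

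**Matched comparison, prevalence equal in both arms, baseline risk 1%, true ratio 2.**
- Case A: (1 − p) cancels and the ratio stays at 2.0.
- Case B: [p + (1 − p) × 0.02] / [p + (1 − p) × 0.01].
  - p = 1%: 2.98/1.99 = 1.50
  - p = 3%: 4.94/3.97 = 1.24
  - p = 5%: 6.90/5.95 = 1.16

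**Multivariable Cox model in Case A.** With no events among dialysis patients, the dialysis coefficient runs to minus infinity. These patients then carry zero weight in every risk set, so the adjusted hazard ratio equals the one from the restricted population. A simulation with assumed inputs (40,000 versus 4,600 patients, prevalence 3% versus 1%, baseline risk 1%, true hazard ratio 2, death competing) gave 1.8563 for both. The unadjusted value was 1.889, and 1.889/1.8563 = 1.02, in line with the crude shift above.

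**Numbers a restriction would remove.** At 1% to 2% of 4,600 COVID-19 survivors: 46 to 92. At 1% to 5% of the 315,000 pre-pandemic survivors: 3,150 to 15,750.

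**The case against.** The strongest reply is that the outcome wording already implies new cases. No section says continuing dialysis counts, and counting it would go against the words used. On that natural reading the bias is negligible, and the listed covariate does for the multivariable hazard ratio what a restriction would do. This stands, and it limits the point. Two things remain. The wording states an intention that no rule carries out. And even on that reading the denominators and unadjusted models include people with no possible event, and the model carries a coefficient that cannot be estimated.

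Two stronger readings are tempting. A reader might infer that reported incidence will be 2 to 7 times too high in every cohort. Those multiples come from Case B alone: at p = 1% and r = 1%, 1.99/1.00 is about 2; at p = 3% and r = 0.5%, 3.49/0.50 is about 7. The documents do not say that Case B will be used, and they supply neither input. A reader might also infer that adjustment achieves nothing. That is wrong in Case A, as shown above.

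It is also fair to say that the event itself lacks a stated data source, code set or duration rule. The restriction does not settle that.

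**Conclusion.** The point holds in a limited form. The plan specifies whole cohorts plus a covariate for an outcome that some cohort members cannot newly have. The consequence ranges from trivial to serious according to how ongoing dialysis is coded. If it is never counted, there is a 1% to 3% relative dilution, a crude ratio of about 1.02, and an essentially unaffected adjusted hazard ratio. If it is counted, the crude ratio is about 0.50 where the truth is 1.00 (1% versus 3%, risk 1%), and a true doubling shows as about 1.24 after matching at 3% prevalence. All of these sizes rest on assumed prevalence and incidence.

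The scope is one secondary outcome, reported as an effect size and interval without a p-value (SAP 3.1). The primary mortality outcome is untouched. The change should be made because it is cheap and removes an open choice that could distort or hide the renal result.

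**What to change.** In SAP 5.3.2, with a cross-reference in 5.4, define an at-risk population for this outcome only: patients without established dialysis dependence or end stage renal failure before the index ICU admission. Identify them from the dialysis flag in SAP 5.2, the linked UK Renal Registry, and the five-year look-back described in protocol 7.3 and 12.1. Do not exclude patients whose earlier renal replacement was temporary and who recovered, since they remain at risk.

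Apply the restriction to the descriptive, unadjusted, matched and multivariable renal analyses. Re-match within the restricted set, drop the dialysis covariate from that propensity score and model, and report the number removed from each cohort.

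The cost is a short addition to the SAP, one extra match, and slightly smaller cohorts for one secondary outcome. All other outcomes keep the full cohorts, and no new data are needed.
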